3.2 Exclusion Criteria

Patients who meet any of the following criteria will be excluded from study entry:

3.2.1 **Exclusion criteria for Parts A and B (HER2-negative) and Part Z (HER2-positive) cohorts:**

1. Treatment with any of the following:
 - Any systemic anti-cancer chemotherapy, small molecule, biologic, hormonal agent, or immune checkpoint inhibitor therapy from a previous treatment regimen or clinical study within 21 days prior to the first dose of patritumab deruxtecan
 - Prior treatment with any HER3-targeting agent
 - Major surgery (excluding placement of vascular access) within 4 weeks of the first dose of study drug treatment
 - Radiotherapy treatment to more than 30% of the bone marrow or with a wide field of radiation within 4 weeks of the first dose of study drug treatment, or palliative radiation therapy within 2 weeks of the first dose of study drug treatment
 - Chloroquine /hydroxychloroquine ≤ 14 days prior to the first dose of study drug treatment
2. Has any hypersensitivity to drug substances or inactive ingredients in drug product
3. Has any history of ILD (including pulmonary fibrosis or radiation pneumonitis), has clinically significant ILD, or is suspected to have such disease by imaging during screening. If imaging findings are unlikely to indicate a history of pneumonitis, then the

CONFIDENTIAL

Investigator should discuss the considerations with the Medical Monitor about potential enrollment and record the reasoning in the source documentation

4. Clinically severe pulmonary compromise (based on Investigator's assessment) resulting from intercurrent pulmonary illnesses including, but not limited to:
 - a. any underlying pulmonary disorder (e.g., pulmonary emboli, severe asthma, severe chronic obstructive pulmonary disease, restrictive lung disease, pleural effusion)
 - b. any autoimmune, connective tissue or inflammatory disorder with pulmonary involvement (e.g., rheumatoid arthritis, Sjögren's syndrome, sarcoidosis)

OR prior pneumonectomy

5. With the exception of alopecia, any unresolved toxicities from prior therapy greater than Common Terminology Criteria for Adverse Events (CTCAE) Grade 1 or baseline at the time of starting study treatment. Note: patients with chronic Grade 2 toxicities who are asymptomatic or adequately managed with stable medication may be eligible with approval by the Medical Monitor.
6. Leptomeningeal metastases or evidence of spinal cord compression or brain metastases, defined as being clinically active and symptomatic, or requiring therapy with corticosteroids or anticonvulsants to control associated symptoms. Patients with clinically inactive or treated brain metastases who are asymptomatic (i.e., without neurologic signs or symptoms and do not require treatment with corticosteroids or anticonvulsants) may be included in the study. Patients must have a stable neurologic status for at least 2 weeks prior to Cycle 1 Day 1.
7. Women who are pregnant, nursing, or plan to become pregnant while in the study and for at least 7 months after the last administration of study treatment
8. Men who plan to father a child while in the study and for at least 7 months after the last administration of study treatment
9. Uncontrolled or significant cardiovascular disorder prior to Cycle 1 Day 1, including:
 - Mean resting corrected QT interval using Fridericia's formula (QTcF) prolongation to >470 ms for females and >450 ms for males in three successive screening measurements
 - Patients with a left ventricular ejection fraction (LVEF) <50%
 - Resting systolic blood pressure >180 mmHg or diastolic blood pressure >110 mmHg).
 - Documented myocardial infarction within 6 months.
 - Congestive heart failure (New York Heart Association ≥ Grade 2 [Appendix D]) within 28 days
10. Has known clinically significant corneal disease from prior therapies such as drug-induced keratitis
11. Is receiving chronic systemic corticosteroids dosed at >10 mg prednisone or equivalent anti-inflammatory activity or any form of immunosuppressive therapy prior to Cycle 1

CONFIDENTIAL

Day 1. Patients who require use of bronchodilators, inhaled or topical steroids, or local steroid injections may be included in the study.

12. As judged by the Investigator, any evidence of severe or uncontrolled systemic diseases, including uncontrolled hypertension, uncontrolled diabetes mellitus, active bleeding diatheses, or active infection, including hepatitis B, hepatitis C, and human immunodeficiency virus. Screening for chronic conditions is not required.
13. Presence of other active invasive cancers other than the one treated in this study within 3 years prior to screening, except appropriately treated basal cell carcinoma of the skin, in situ carcinoma of uterine cervix, or other local tumors considered cured by local treatment
14. Psychological, familial, sociological, or geographical conditions that do not permit compliance with the protocol and/or follow-up procedures outlined in the protocol.

3.2.2 Additional exclusion criteria only for Parts A and B (HER2-negative) cohorts:

15. Patients with HER2+ breast cancer per ASCO-CAP guidelines
16. **Part A only:** Prior treatment with an antibody drug conjugate that consists of an exatecan derivative that is a topoisomerase I inhibitor (e.g., trastuzumab deruxtecan, DS-1062a [datopotamab deruxtecan], and DS-7300a [B7-H3 DXd-ADC])
17. **Part B patients only:** Prior treatment with trastuzumab deruxtecan, sacituzumab govitecan, and/or datopotamab deruxtecan with any of the following:
 - A severe reaction or severe tolerability issues that necessitated stopping treatment with the therapy
 - Any unresolved toxicities from the prior therapy greater than Grade 1, with the exception of alopecia

3.2.3 Additional exclusion criteria only for Part Z (HER2-positive) cohort:

18. Treatment with any of the following:
 - Prior treatment with an antibody drug conjugate that consists of an exatecan derivative that is a topoisomerase I inhibitor except trastuzumab deruxtecan
 - Prior treatment with trastuzumab deruxtecan within 4 weeks prior to the first dose of patritumab deruxtecan
19. Uncontrolled or significant cardiovascular disease, including history of myocardial infarction within 6 months before enrollment
20. A severe reaction or severe tolerability issues that necessitated stopping treatment with trastuzumab deruxtecan
21. Any unresolved toxicities from prior therapy with trastuzumab deruxtecan

CONFIDENTIAL

3.3 Discontinuation from Study Treatment

Patients will be discontinued from study treatment for any of the following reasons:

- Disease progression (Patients who are receiving clinical benefit in the opinion of the treating Investigator may be allowed to stay on study after consultation with the Medical Monitor.)
- Irreversible or intolerable toxicity or abnormal laboratory values thought to be related to drug toxicity
- Conditions requiring therapeutic intervention not permitted by the protocol
- Intercurrent illness (this will be at the Investigator's discretion)
- Inability of the patient to comply with study requirements
- Patient lost to follow-up
- Patient requests to discontinue treatment
- Patient withdraws consent from study treatment or study participation altogether
- Pregnancy
- Study termination

After discontinuation from protocol treatment, patients must be followed for adverse events (AEs) for 40 days (+7 days) after their last dose of study drug. All new AEs occurring during this period must be reported and followed until resolution, unless, in the opinion of the Investigator, these values are not likely to improve because of the underlying disease. In this case, the Investigator must record his or her reasoning for this decision in the patient's medical records.

All patients who have Grade 3 or 4 laboratory abnormalities (per National Cancer Institute [NCI] CTCAE Version 5.0) at the time of discontinuation must be followed until the laboratory values have returned to Grade 1 or 2, unless it is, in the opinion of the Investigator, not likely that these values are to improve. In this case, the Investigator must record his or her reasoning for making this decision in the patient's medical records.

4. STUDY REGISTRATION

The patient must willingly consent after being informed of the procedures to be followed, the experimental nature of the treatment, and the potential benefits, alternatives, side-effects, risks, and discomforts. Human protection committee/institutional review board (IRB) approval of this protocol and any associated ICFs is required. Eligible patients who wish to participate in the study will be enrolled into the study.

Registration must occur prior to the initiation of protocol therapy. Patients eligible to participate in the study may be enrolled by each site following the patient registration instructions provided by the Sarah Cannon Development Innovations, LLC (Development Innovations) study contact. Patient registration follow-up and/or confirmation will be provided via email within approximately 48 hours or by the next business day.

CONFIDENTIAL

5. STUDY DESIGN

This is a Phase II open-label study of patritumab deruxtecan in patients with MBC and will be conducted in 3 parts. Part A will enroll up to 60 patients with HER2- MBC. All enrolled patients will undergo pre-treatment biopsies (unless a biopsy was done within 2 months prior to consent) to determine if patients with expression of the following biomarkers as determined by IHC (ER/PR/HER2/HER3) show response to treatment after all patients in Part A have completed 2 tumor assessments. Blood samples and on-treatment biopsy samples will be collected from all patients for additional correlative analyses.

Part B will enroll an additional 20 patients into each of 2 subgroups that were defined from the Part A (based on ER/PR/HER2/HER3 expression) evaluation of biomarker expression in pre-treatment biopsy samples or in tissue from a biopsy done within 2 months prior to consent. A total of up to 40 patients will be enrolled into the following 2 Part B subgroups:

- MBC HR+, HER2-, regardless of HER3 expression, post-trastuzumab deruxtecan and/or sacituzumab govitecan therapy
- mTNBC, regardless of HER3 expression, post-sacituzumab govitecan and/or datopotamab deruxtecan therapy

[figure not shown]
Patients enrolled in Part A will be included along with Part B patients of their respective subgroups in the final statistical analysis for efficacy.

Part Z will enroll an additional 21 patients with HER2+ MBC. All enrolled patients will undergo pre-treatment biopsies (unless a biopsy was done while on or after trastuzumab deruxtecan therapy within 3 months prior to consent and tissue from this biopsy is available) for biomarker analysis. Blood samples and on-treatment biopsy samples will be collected from all patients for additional correlative analyses, unless not technically feasible or unsafe for the patient after discussion with the Medical Monitor. PK and ADA blood samples will be collected from all patients.

The study schema is presented in Figure 1.

[figure not shown]
Figure 1 Study Schema Parts A and B

CONFIDENTIAL

CONFIDENTIAL

Figure 2 Study Schema Part Z

All eligible patients will receive patritumab deruxtecan 5.6 mg/kg intravenous (IV) on Day 1 of each cycle (every 3 weeks [Q3W]). Patients will have computed tomography (CT) scans every 6 weeks (± 5 days) from Cycle 1 Day 1 for the first 6 months, then every 9 weeks (± 5 days) thereafter. Patients will be allowed to continue on therapy as long as they have no disease progression, have not withdrawn from the study, have not met other protocol-defined criteria for treatment discontinuation, and are considered by the Investigator to still be receiving clinical benefit. Patients who are receiving clinical benefit in the opinion of the treating Investigator may be allowed to stay on study after disease progression after consultation with the Medical Monitor.

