3. STUDY PATIENT POPULATION AND DISCONTINUATION

3.1 Inclusion Criteria

Patients must meet the following criteria in order to be included in the research study:

3.1.1 Inclusion criteria for Part A and B (HER2-negative) and Part Z (HER2-positive) cohorts:

1. Written informed consent, according to local guidelines, signed and dated by the patient or by a legal guardian prior to the performance of any study-specific procedures, sampling, or analyses

CONFIDENTIAL

2. Women and men at least 18 years-of-age at the time of signature of the informed consent form (ICF)
3. Histologically documented locally advanced or metastatic breast cancer
4. Triple-negative breast cancer (TNBC) patients should have received at least 1 but no more than 5 prior lines of chemotherapy in the metastatic setting
5. **Parts A and B patients only:** Patients with HR+ HER2-negative MBC should have received prior treatment with endocrine therapy +CDK 4/6 inhibitor. No limit to prior endocrine therapy regimens, but no more than 2 prior chemotherapy regimens in the metastatic setting are allowed. HR+ = ER and/or PgR positivity that are defined as $\geq 1\%$ of cells expressing HR via IHC analysis. HER2 negativity is defined as either of the following: IHC 0, IHC 1+, or IHC 2+/in situ hybridization (ISH) negative.
6. **Part B patients only:** Patients with HER2-negative MBC will be included into one of the following 2 subgroups: 1) MBC HR+, HER2-, regardless of HER3 expression, who have received trastuzumab deruxtecan and/or sacituzumab govitecan, or, 2) mTNBC, regardless of HER3 expression, who have received sacituzumab govitecan and/or datopotamab deruxtecan.
7. **Part Z patients only:** should have documented HER2-positive expression as per American Society of Clinical Oncology – College of American Pathologists guidelines based on local testing.
8. **Part Z patients only:** should have had prior treatment with at least 2 anti-HER2 therapies, 1 of which must be trastuzumab deruxtecan. These patients must have experienced disease progression after receiving trastuzumab deruxtecan.
9. At least 1 measurable lesion per Response Evaluation Criteria in Solid Tumors (RECIST) v1.1 (bone-only disease excluded)

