10.2 Sample Size Considerations

Sixty patients will be enrolled into Part A, and the sizes of the biomarker expression-defined subgroups will not be restricted. Evaluation of biomarker expression-defined subgroups to carry forward into Part B will be based on evaluation of overall response rate (ORR), PFS-6, and results from correlative tests.

Patients in the subgroups from Part A that are expanded in Part B will be included in a combined subgroup for presentation (e.g., if 12 ER high/HER-3 high patients are treated in Part A, and that subgroup treats 20 additional patients in Part B, they would be added to the affiliated Part B subgroup for a total of 32 in analysis). Part Z will enroll an additional 21 patients with HER2+ MBC.

PFS-6 will be a binary endpoint with patients surviving progression-free for at least six month considered successes; otherwise, patients will be considered failures (including patients who withdraw from the study prior to six months). The ORR and six-month PFS will be presented with two-sided 95% confidence intervals (CIs) (calculated based on the Clopper-Pearson method). Table 5 below shows the precision of the estimates for the two endpoints across a range of sample sizes and ORR or PFS-6 rates.

Table 5 Projected CIs for ORR and PFS-6

Approximate ORR or PFS-6	n	Percentage (95% CI) [†]	Width of 95% CI [†]
0.20	20	0.20 (0.06, 0.44)	0.38
	25	0.20 (0.07, 0.41)	0.34
	30	0.20 (0.08, 0.39)	0.31
	35	0.20 (0.08, 0.37)	0.28
	40	0.20 (0.09, 0.36)	0.27
0.30	20	0.30 (0.12, 0.54)	0.42
	25	0.32 (0.15, 0.54)	0.39
	30	0.30 (0.15, 0.49)	0.35
	35	0.31 (0.17, 0.49)	0.32
	40	0.30 (0.17, 0.47)	0.30
0.40	20	0.40 (0.19, 0.64)	0.45
	25	0.40 (0.21, 0.61)	0.40

CONFIDENTIAL

Approximate ORR or PFS-6	n	Percentage (95% CI) [†]	Width of 95% CI [†]
	30	0.40 (0.23, 0.59)	0.37
	35	0.40 (0.24, 0.58)	0.34
	40	0.40 (0.25, 0.57)	0.32
0.50	20	0.50 (0.27, 0.73)	0.46
	25	0.52 (0.31, 0.72)	0.41
	30	0.50 (0.31, 0.69)	0.37
	35	0.51 (0.34, 0.69)	0.35
	40	0.50 (0.34, 0.66)	0.32

[†]Based on Clopper-Pearson.

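### Part B subgroups defined by prior ADC are pooled with Part A patients who can match them only through prior sacituzumab govitecan, and no result by Part or prior ADC is planned

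*Combined protocol and SAP*

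**What the plan says.** The pooling rule appears in the Synopsis and in Section 5: "Patients enrolled in Part A will be included along with Part B patients of their respective subgroups in the final statistical analysis for efficacy". Section 10.2 repeats it: "Patients in the subgroups from Part A that are expanded in Part B will be included in a combined subgroup for presentation". Its worked example takes 12 Part A patients with high ER and high HER3 and adds 20 from Part B: "they would be added to the affiliated Part B subgroup for a total of 32 in analysis". Section 10.2 also leaves the Part A subgroup sizes unrestricted within a total of 60.

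The two Part B subgroups, 20 patients each, are "MBC HR+, HER2-, regardless of HER3 expression, post-trastuzumab deruxtecan and/or sacituzumab govitecan therapy" and "mTNBC, regardless of HER3 expression, post-sacituzumab govitecan and/or datopotamab deruxtecan therapy". Inclusion criterion 6 in Section 3.1.1 makes the prior ADC an entry requirement; for the HR+ subgroup it takes patients "who have received trastuzumab deruxtecan and/or sacituzumab govitecan".

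For Part A only, exclusion 16 in Section 3.2.2 bars "Prior treatment with an antibody drug conjugate that consists of an exatecan derivative that is a topoisomerase I inhibitor" and gives trastuzumab deruxtecan and datopotamab deruxtecan among its examples. It does not name sacituzumab govitecan.

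Section 10.4.2 plans efficacy results overall and by biomarker-defined subgroup, with Clopper-Pearson intervals for ORR and PFS-6. It specifies no result by Part or by prior ADC. Section 1.1.5 presents activity after progression on an ADC as a question of interest and mentions both cross-resistance and durable responses to a later ADC.

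**The concern.** For trastuzumab deruxtecan and datopotamab deruxtecan, the exposure that qualifies a patient for Part B disqualifies a patient from Part A. If Part A patients join a Part B subgroup because they share its receptor status, the combined group differs in the feature that now defines that subgroup. The pooled proportion is then a weighted average of two rates, with a weight set by how many Part A patients happened to fall in each receptor group. Its interval describes neither population unless the rates are equal.

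This is an estimation study with no null rate and no test, so the estimates and intervals are the result. As written, the plan does not commit to an ORR or PFS-6 for HER2-negative patients previously treated with an ADC, although Part B was set up to enrol them.

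**Working it through.** **Reproducing the plan's figures.** Exact Clopper-Pearson limits reproduce all 20 rows of Table 5 to rounding; for example, 4/20 gives 0.20 (0.06, 0.44), width 0.38. The pooled example also reproduces: 12 + 20 = 32, of which Part A is 12/32 = 37.5%.

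**Who can match.**

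| Prior ADC | Part A | Part B, HR+/HER2- | Part B, mTNBC |
|---|---|---|---|
| Trastuzumab deruxtecan | barred | qualifies | not listed |
| Datopotamab deruxtecan | barred | not listed | qualifies |
| Sacituzumab govitecan | not named in exclusion 16 | qualifies | qualifies |
| None | allowed | does not qualify | does not qualify |

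The only overlap is prior sacituzumab govitecan. The documents do not say how many Part A patients had it.

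**Inputs for the size of the effect.** From the documents: nB = 20 per subgroup, two-sided 95% Clopper-Pearson, and nA = 12 from the Section 10.2 example. Assumed: nA = 20, 30 or 40, and true rates pA (Part A) and pB (post-ADC) taken from the Table 5 range of 0.20 to 0.50. If all 60 Part A patients are enrolled and each is either HR+ or triple-negative, the two values of nA sum to 60, so at least one is 30 or more.

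**Formulas.** Expected pooled rate = (nA × pA + 20 × pB) / (nA + 20). Coverage = probability that the Clopper-Pearson interval on nA + 20 patients contains pB, from the exact convolution of Bin(nA, pA) and Bin(20, pB).

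For nA = 12, pA = 0.40 and pB = 0.20, the expected rate is (4.8 + 4.0)/32 = 0.275. The interval on 32 patients contains 0.20 when the pooled responder count is 2 to 11, which has probability 0.862.

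| pA v pB | Quantity | nA = 12 | 20 | 30 | 40 |
|---|---|---|---|---|---|
| 40% v 20% | expected pooled rate | 28% | 30% | 32% | 33% |
| | coverage of 20% | 86% | 71% | 57% | 34% |
| 30% v 20% | expected pooled rate | 24% | 25% | 26% | 27% |
| | coverage of 20% | 94% | 90% | 87% | 77% |
| 40% v 30% | expected pooled rate | 34% | 35% | 36% | 37% |
| | coverage of 30% | 95% | 93% | 91% | 83% |

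With pA = pB there is no bias; at 30% in both, coverage is 96% to 97%.

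**One concrete outcome.** With 5/12 responders in Part A and 4/20 in Part B, the plan reports 9/32 = 0.28 (0.14, 0.47). Part B alone gives 0.20 (0.06, 0.44).

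The model gives every Part A patient the same rate pA. Part A patients with prior sacituzumab govitecan may respond more like Part B, which would reduce the effect by an unknown amount.

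**The case against.** **The target is not a listed objective.** For HER2-negative disease, Table 1 names ORR and PFS-6 in HER2-negative MBC; the only post-ADC objective is for Part Z. A reader might infer that the pooling defeats the primary objective. The documents do not support that: the post-ADC question for these patients comes from the rationale in Section 1.1.5 and from the Part B entry criteria. What stands is that Part B selects on prior ADC and no result is specified for the patients so selected.

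**The pooling may be meant narrowly.** The reference to respective subgroups in Section 5 comes after the two prior-ADC definitions and could mean only Part A patients who fit them. The text does not say so. The ER-high/HER3-high example and the biomarker-defined wording in Section 10.4.2 point to matching on expression. Even on the narrow reading, the added patients would all qualify through sacituzumab govitecan, and the rule would need to be written down.

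**Part A is not ADC-naive.** A reader might infer from exclusion 16 that it is. Sacituzumab govitecan is not named there, so that description is too strong.

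**The direction is not known.** A reader might infer that pooling must inflate the post-ADC rate. That requires a lower rate after an ADC. Section 1.1.5 mentions cross-resistance, but also durable responses, particularly with a different antibody target. The 42.9% ORR in Section 1.1.4 is no firm anchor for Part A: it comes from 42 patients at 1.6 to 8.0 mg/kg in a study of HER3-positive tumours.

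**The harm is recoverable.** This is fair. Section 10.2 describes the combined subgroup as being for presentation, Part A is examined at the interim analysis, and a later split needs no new patients. But the Synopsis and Section 5 place the pooling in the final efficacy analysis, and a split chosen after the results are known is weaker than a planned one.

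**Conclusion.** The point holds in this form: the plan pools Part A with Part B subgroups that Part A patients can match only through prior sacituzumab govitecan, and it specifies no ORR or PFS-6 by Part or prior ADC. The pooled result is a mixture whose weights are not controlled.

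The size depends on rates that the documents do not give. Across the assumed cases with a gap, the shift in the expected estimate runs from about 4 points (10-point gap, 12 Part A patients) to about 13 points (20-point gap, 40 Part A patients), and coverage of the post-ADC rate from 95% down to 34%. At the protocol's own example size of 12, coverage is 86% with 40% v 20% and 94% with 30% v 20%, so the effect there is moderate or small. It is zero if prior ADC exposure does not affect response. The mismatch in definitions does not depend on any of these assumptions.

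**What to change.** In the Synopsis and Sections 5, 10.2 and 10.4.2:

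- Report ORR and PFS-6 for each Part B subgroup alone (n=20, Clopper-Pearson interval) as the post-ADC result.
- Report Part A separately by receptor status.
- Pool only Part A patients with a documented qualifying prior ADC, or show the wider pool as a labelled supportive table split by prior ADC.
- Replace the 12 + 20 = 32 example with one that fits the current subgroup definitions.

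Section 10.4.2 must be changed with the others, because it sets the efficacy output. Part B should be described as patients who have received an ADC: inclusion 6 requires receipt, whereas inclusion 8 for Part Z requires progression, so Part B alone does not fully isolate the population described in Section 1.1.5.

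The change needs no new patients or data. The cost is precision: at n=20 the interval width is 0.38 to 0.46 for rates of 0.20 to 0.50, as Table 5 already shows. A pooled n=50 would give 0.24 (10/50) to 0.29 (25/50), but for a mixed population.
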